#### 9.1.2 Analysis of the primary efficacy endpoint

#### Primary efficacy endpoint:

• Changes in blood haemoglobin level (g/L) after 12-weeks of iron-deficiency anaemia treatment (during the final visit), as compared with the baseline value (the screening visit) between the study groups.

Analysis of covariance (ANCOVA) will be used as the main method of assessment of the primary endpoint, with baseline haemoglobin value being a covariate and four fixed factors (treatment group, gender, weight and baseline Hb level (80–94 g/L vs 95–110 g/L). Unrestricted least significant differences (LSD) method will be applied to the ANCOVA results with the calculation of least-square (LS) means with 95% CI for LS means for the difference between the study groups. Non-inferiority will be confirmed if the upper limit of the two-sided 95% confidence interval for LS mean will not exceed the pre-defined non-inferiority margin of 5 g/L.

#### 9.1.3 Analysis of the secondary effecacy endpoints

#### Secondary efficacy endpoints:

All secondary efficacy analysis will be considered explorative, therefore, no multiplicity correction will be done for any tests, and no formal power calculation will be provided for the test results.

• Absolute values and changes (compared to baseline) of blood hemoglobin level (g/L) after 12 weeks of treatment (during the final visit) between the study groups.

Values at individual time points and values of change between the individual time points will be compared using the t-test or Mann-Whitney test depending on the normality of the distribution (which will be tested using Shapiro-Wilk test).

Additionally, it is planned to use ANCOVA for analysis of changes in the assessed parameters over time where group will be a fixed factor, screening hemoglobin level will be a covariate, and hemoglobin level at Week 12 will be a response variable.

• Changes in average values of iron metabolism parameters (ferritin, transferrin, percent transferrin saturation, serum iron) during the treatment period (from screening till the final visit) in the study groups.

Values at individual time points (baseline and Week 12) and values of change between the individual time points (baseline and Week 12) will be compared using the t-test or Mann-Whitney test depending on the normality of the distribution (which will be tested using Shapiro-Wilk test).

• The percentage (%) of subjects with response to the therapy, determined as an increase in hemoglobin level by 20 g/L and more after 12-weeks of treatment (from screening till the final visit) in the study groups.

Comparison between the two groups will be performed using the Fisher's exact test or chi-square test depending on the number of expected observations per cell (<5 or  $\geq$ 5). Two-sided 95% confidence interval will be calculated using exact Clopper-Pearson method.

These changes will be compared between the groups using the t-test or Mann-Whitney test depending on the normality of the distribution (which will be tested using Shapiro-Wilk test).

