#### Safety Measurements

Safety evaluation will include:

1) Determination of the total number, frequency and severity of:

- I. adverse events (AEs) irrespective of their relation to treatment;
- II. AEs related or possibly related to the treatment received;
- III. AEs requiring termination of the therapy.

2) Complaints on digestive system disorders (defined through MedDRA SMQ for the corresponding symptoms), considered as related to the study therapy by the investigator, will be analyzed separately.

Descriptive statistics will be used for presentation of the result. Comparison of all AE incidence between the study groups will be performed using the Fisher's exact test or chi-square test depending on the number of expected observations per cell (<5 or  $\geq 5$ ), and comparison of intensity (and possible causal relationship between the treatment received and the AE) will be performed using Cochrane-Armitage trend test for the ordered categorical data.

3) Changes in laboratory test results (assessed in central laboratory) over time and frequency of abnormal test results (according to the normal ranges of central laboratory) will be summarized by group and also compared by group using corresponding tests for quantitative data and qualitative data (see below).

4) Changes in vital signs over time and frequency of abnormal physical examination findings will be summarized by group and also compared by group using corresponding tests for quantitative data and qualitative data (see below).

Quantitative data will be compared using the t-test or Mann-Whitney test depending on the normality of the distribution (which will be tested using Shapiro-Wilk test).

Qualitative data will be compared using the Fisher's exact test or chi-square test depending on the number of expected observations per cell (<5 or  $\geq 5$ ).

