8.2. Analysis of the secondary endpoint

- Absolute values and changes in hemoglobin level (g/L) after 4, 8, and 12 weeks of therapy (determined at the final visit) between the study groups.
- Changes in iron metabolism parameters mean values (ferritin, transferrin, percent transferrin saturation, serum iron) during the therapy period (from the screening to the study end visit) in the study groups.
- The responder rate (%) was determined as an increase in the hemoglobin level by ≥ 20 g/L after 12 weeks of treatment (from screening to the study end visit) in the study groups.

The data will be checked for compliance with the normal distribution law using the Shapiro-Wilk test.

Intergroup comparison of secondary endpoints related to quantitative scales will be performed using Student's t-test for independent samples if the data correspond to the normal distribution law; otherwise, the Mann–Whitney U test will be applied to independent samples.

Intergroup comparisons of secondary endpoints related to categorical scales will be performed using Pearson's chi-square test if the number of points in each cell of the crosstab is ≥ 5 , or Fisher's exact test if at least one of the crosstab cells contains < 5 points.

The dynamics will be assessed using ANOVA methods with repeated measurements if the data correspond to the normal distribution; otherwise, the Friedman test will be applied.

9. Safety analysis

Safety evaluation of the study therapy will be performed throughout the study and will be based on the detection of any adverse events occurring during the study. The following will be performed:

- Physical examination, including measurement of blood pressure and heart rate, and gastrointestinal disorders identification (at the screening, during the second visit, and the final visit).
- Complete blood count (at screening and in 4, 8, and 12 weeks of treatment);
- Blood biochemistry (at screening and after 12 weeks of treatment);
- Clinical urinalysis, pregnancy test (at screening and in 12 weeks);
- Registration of concomitant therapy (at each visit).

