Appendix 1. Table layouts

PRIMARY ENDPOINT

Parameter	Coef.	Standard error	t -value	p -value	С	2I
Constant (intercept)						
Group R versus Group T						
Gender M versus F						
Weight						
Base hemoglobin factor (80–94 g/L compared to 95–110 g/L)						
Hemoglobin level at screening						
Interactions						

SECONDARY ENDPOINTS

Table 1. Hemoglobin, frequency analysis of the treatment efficacy after 12 weeks

Hemoglobin (g/L)					
Group	Parameter	Value			
	Total observations				
$R - Maltofer^{\mathbb{R}}$	Responders, n				
	Responders, %				
	95% CI				
	Total observations				
T – Ferrum Lek®	Responders, n				
	Responders, %				
	95% CI				
Group comparison	Pearson's chi-square test, p-value				

Table 2. Results of analysis of variance

Coefficients	Evaluation	Standard error	t-value	p-value
(Intercept)				
V1_CB_LBORRES_HB				
(Hemoglohin level at screening)				
Group T – Ferrum Lek [®]				
(Test to reference group factor)				

Table 3. Hemoglobin, absolute values, g/L

Hemoglobin (g/L)						
Group	Parameter	Screening	Week 4	Week 8	Week 12	
	Number of observations					
	Number of missing values					
	Mean value					
R – Maltofer®	95% CI					
	Standard deviation					
	Median					
	Minimum value					
	Maximum value					

	1st quartile		
	3rd quartile		
	Interquartile range		
	p-value (Shapiro–Wilk test)		
	Number of observations		
	Number of missing values		
	Mean value		
	95% CI		
	Standard deviation		
	Median		
T – Ferrum Lek [®]	Minimum value		
	Maximum value		
	1st quartile		
	3rd quartile		
	Interquartile range		
	p-value (Shapiro–Wilk test)		
Group	Criterion		
comparison	p-value		

SOP-05-02_RF01 Statistical Analysis Plan_01APR2020_3.0

Table 4. Hemoglobin, changes, g/L

Hemoglobin (g/L)						
Group	Parameter	Week 4 – Screening	Week 8 – Screening	Week 12 – Screening		
	Number of observations					
	Number of missing values					
	Mean value					
	95% CI					
	Standard deviation					
	Median					
R – Maltofer®	Minimum value					
	Maximum value					
	1st quartile					
	3rd quartile					
	Interquartile range					
	p-value (Shapiro–Wilk test)					
	Number of observations					
	Number of missing values					
	Mean value					
T − Ferrum Lek®	95% CI					
	Standard deviation					
	Median					
	Minimum value					

STATISTICAL ANALYSIS PLAN

	Maximum value		
	1st quartile		
	3rd quartile		
	Interquartile range		
	p-value (Shapiro–Wilk test)		
Group comparison	Criterion		
	p-value		

Table 5. Blood serum iron, absolute values, μ mol/L

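### A Shapiro-Wilk result on the trial data picks the test for continuous secondary endpoints, so the hypothesis can change between visits, and no between-group difference with CI is specified for haemoglobin at Weeks 4 and 8 or for the iron parameters

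*Protocol*

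**What the plan says.** **Where the rule applies.**

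- Protocol 9.1.3, haemoglobin, at each visit and for each change between visits: t-test or Mann-Whitney, chosen "depending on the normality of the distribution (which will be tested using Shapiro-Wilk test".
- Protocol 9.1.3, iron parameters: the same rule, restricted to "Values at individual time points (baseline and Week 12) and values of change between the individual time points (baseline and Week 12".
- SAP 8.2: "The data will be checked for compliance with the normal distribution law using the Shapiro-Wilk test". The t-test is used if the data pass; "otherwise, the Mann–Whitney U test will be applied to independent samples". The haemoglobin endpoint there is "Absolute values and changes in hemoglobin level (g/L) after 4, 8, and 12 weeks of therapy". SAP 8.2 adds a second normality switch, between repeated-measures ANOVA and the Friedman test, for change over time.
- Protocol 4.1, 9.1.4 and the synopsis, safety: "Quantitative data will be compared using the t-test or Mann-Whitney test depending on the normality of the distribution". Protocol 9.1.1 and SAP section 5 use the same rule for baseline comparisons.
- SAP Appendix 1, efficacy Tables 3 to 12: each arm has a row "p-value (Shapiro–Wilk test") in every visit column, followed by a row naming the criterion used and a row for its p-value.

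**Where it does not apply.** The primary endpoint is analysed by a pre-specified ANCOVA (Protocol 9.1.2, SAP 8.1). Protocol 9.1.3 and SAP efficacy Table 2 add an ANCOVA of Week 12 haemoglobin. The responder rate uses chi-square or Fisher's exact test. Protocol 9.1 fixes the descriptive summaries for every continuous variable, including mean with 95% CI, SD, median and interquartile range. Protocol 9.1.3 calls all secondary efficacy analyses exploratory, without multiplicity correction.

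**The concern.** The t-test compares means. Mann-Whitney asks whether a value from one arm tends to exceed a value from the other. The two agree when both arms share one shape, and need not otherwise. If a normality test on the same data decides which is used, haemoglobin may be compared on means at Week 4 and on ranks at Week 8. A significant result beside a non-significant one could then reflect a change of test.

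The rule is also incomplete: neither document says what happens when one arm passes Shapiro-Wilk and the other fails. Nor does either candidate test come with a specified between-group estimate, so at Weeks 4 and 8 the planned comparison is a p-value without a difference in g/L and its interval.

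**Working it through.** **1. The sample size behind the argument.** Inputs from Protocol 9.3: SD 15 g/L, margin 5 g/L, true difference 0, 80% power (z = 0.8416), final critical value 1.976.

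n per arm = 2 × [15 × (1.976 + 0.8416) / 5]² = 142.9, so 143, as stated. A two-look check at 70% information with bounds 2.628 and 1.976 gives 80.2% power and one-sided alpha 0.0250. (One-sided 0.05, as the text words it, would give 112; the 143 rests on one-sided 0.025.)

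**2. Does the t-test need a normality screen at this size?** The documents give no distribution shapes, so those below are assumptions, the same in both arms. Shapiro-Wilk uses 0.05, following the general level in Protocol 9.4 and SAP 3.1. Rejection in either arm is assumed to trigger Mann-Whitney. There were 20,000 runs for the t-test and 5,000 for the other columns, at 143 per arm and nominal two-sided 0.05.

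| Shape | t-test error | Switch to Mann-Whitney | Error of the two-stage rule |
|---|---|---|---|
| Normal | 0.052 | 0.096 | 0.057 |
| Gamma, skewness 0.5 | 0.049 | 0.803 | 0.052 |
| Gamma, skewness 0.7 | 0.050 | 0.982 | 0.053 |
| Gamma, skewness 1 | 0.050 | 1.000 | 0.050 |
| t, 5 df | 0.050 | 0.904 | 0.051 |
| Lognormal, sigma 0.5 | 0.048 | 1.000 | 0.049 |
| Lognormal, sigma 1 | 0.046 | 1.000 | 0.047 |

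The normal row can be checked by hand: the chance that at least one of two arms fails is 1 − 0.95² = 0.0975, against 0.096 simulated. Monte Carlo standard error at 5,000 runs is √(0.05 × 0.95 / 5,000) = 0.003.

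At 100 per arm, the interim size in Protocol 9.3 and SAP section 11 (Protocol 9.2 says 120), the t-test error is 0.045 to 0.051. The switch rate is 0.100 for normal data, 0.651 at skewness 0.5 and 0.913 at skewness 0.7.

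**3. How often would visits of one endpoint use different tests?** Three visits, assumed correlation 0.6, 143 per arm, 2,000 runs. The visits do not all use the same test in 26% of trials (normal), 59% (skewness 0.25), 41% (skewness 0.5) and 0% (skewness 1).

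**4. Do the hypotheses really differ?** With equal means and SDs but different shapes (4,000 runs), rejection rates at 0.05 are:

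- gamma skewness 1 against normal: t-test 5.0%, Mann-Whitney 10.5%;
- lognormal against normal: t-test 4.9%, Mann-Whitney 22.9%.

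**5. How many comparisons are affected?** The SAP efficacy shells cover five parameters (haemoglobin, serum iron, transferrin, saturation, ferritin), each with four absolute-value columns and three change columns: 5 × (4 + 3) = 35 comparisons whose test is not named in advance.

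**6. Which between-group estimates are specified?**

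| Endpoint | Between-group difference with CI |
|---|---|
| Haemoglobin change, Week 12 | Yes: primary ANCOVA, LS-mean difference in g/L |
| Haemoglobin, Weeks 4 and 8 | None; per-arm summaries and a p-value |
| Iron parameters, any visit | None; per-arm summaries and a p-value |

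The extra Week 12 ANCOVA in efficacy Table 2 has a group coefficient and standard error but no CI column.

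**The case against.** Much can be said for the plan, and most of it stands.

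- A reader might infer that the reported estimate itself depends on the pre-test. It does not: Protocol 9.1 and the SAP shells give means with CI and medians with quartiles per arm whichever test is chosen. Only the criterion and its p-value change.
- A reader might infer that the haemoglobin results are not in g/L, or that visits cannot be compared. SAP efficacy Table 4 gives the mean change in g/L with CI per arm at Weeks 4, 8 and 12. The 5 g/L margin applies only to Week 12, where the primary ANCOVA supplies the difference.
- A reader might infer inflated false-positive rates. With the same shape in both arms the two-stage rule stays at 0.047 to 0.057.
- The rule does not reach every endpoint at every visit. The responder rate is outside it, Protocol 9.1.3 limits iron parameters to baseline and Week 12 (the SAP shells go further), and the biochemistry shells cover at most two visits.
- Several laboratory shells, including one with haemoglobin, have rows for both the t-test and the Wilcoxon-Mann-Whitney p-value. They do not say whether one is left blank or which governs.
- The switch rates come from assumed shapes, and at strong skewness the visits agree because all of them switch.

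The exploratory label answers less than it seems to. It waives multiplicity control; it does not explain why the test is left unnamed in a SAP meant to give the detail behind Protocol section 9.

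**Conclusion.** The point holds in a limited form. The pre-test leaves the hypothesis for a continuous secondary endpoint to be settled by the data, possibly differently at different visits, with no rule for arms that disagree on normality. At about 143 per arm it buys no error control, because the t-test already keeps its size (0.046 to 0.052). The missing between-group difference with CI for haemoglobin at Weeks 4 and 8 and for the iron parameters follows from reading the documents and needs no simulation.

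The size of the switching does need assumptions: gamma, lognormal or t shapes, either-arm rejection at 0.05, and correlation 0.6 between visits. Under them the switch rate runs from about 10% to 100%, and disagreement between visits from 0% to 59%.

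The documents do not support a claim that the primary conclusion is at risk. The consequence is confined to exploratory p-values, with one qualification: Protocol 9.2 and SAP section 11 list secondary endpoints among the results that may inform the interim stopping decision. This is a worthwhile improvement rather than a serious defect.

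**What to change.** 1. Delete the Shapiro-Wilk choice of test in Protocol 9.1.3, 9.1.4, 4.1 and the synopsis, and in SAP 8.2, including the repeated-measures ANOVA/Friedman switch. Align the baseline wording in Protocol 9.1.1 and SAP section 5.
2. Pre-specify baseline-adjusted ANCOVA at each visit for haemoglobin, serum iron, transferrin and saturation. Use the log scale for ferritin and for any other variable named in advance as skewed, and state how values beyond the detection limit enter a log analysis.
3. Report the between-group difference, or ratio on the log scale, with 95% CI at each visit.
4. Keep Mann-Whitney as a labelled sensitivity analysis.
5. In the shells, replace the Shapiro-Wilk and criterion rows with the between-group estimate and CI. Where both p-values are printed, state which is the main one.

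The cost is edits to wording and table shells, plus a small loss of efficiency relative to a rank test if a variable proves heavily skewed. No extra patients, visits or samples are needed.

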#### 9.1.4 Safety parameteres analysis

Safety evaluation will include:

- 1) determination of the total number, incidence and severity of the folowing:
  - I. adverse events (AEs), regardless of their relationship to the treatment;
  - II. AEs associated or potentially associated with the drug;
  - III. AEs leading to discontinuation.

2) Gastrointestinal disorders (determined by means of a standardized MedDRA query for the corresponding symptoms), regarded by the Investigator as related to the study therapy, will be analyzed separately.

Methods of descriptive statistics will be used to represent the results. A comparison of the incidence of new AE cases in the study groups will be performed using the Fisher's exact test or

the chi-square test, depending on the number of proposed observations in one cell (<5 or  $\ge 5$ ), and a comparison of the severity (and the possible causality between the study drug and AE) will be conducted using the Cochran—Armitage test for linear trends for ordered categorical data.

3) Changes in the results of laboratory studies (conducted in the central laboratory) over time and the incidence of abnormal results of studies (based on the reference values of the central laboratory) will be summarized by group, and a comparison will be made between the groups using appropriate tests for quantitative and qualitative data (see below).

4) Changes in the vital signs over time and the incidence of pathological abnormalities revealed during physical examination will be summarized by group, and a comparison will be made between the groups using appropriate tests for quantitative and qualitative data (see below).

Comparison of quantitative data will be conducted using the t-test or the Mann—Whitney test, depending on the distribution normality (which will be estimated using the Shapiro—Wilk test).

Qualitative data will be compared using the exact Fisher's exact test or the chi-square test, depending on the number of proposed observations in one cell (<5 or  $\geq 5$ ).

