### 4.4.2 Blinding

The study treatment is prescribed openly. Blinding within this study is not planned.

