## 4.10 Storing and unblinding of randomization codes

The table with treatment randomization codes will be stored in Sponsor's company, the access to this information will be restricted to designated persons. Procedures of unblinding of randomization codes are not applicable within this study, as the blinding of treatment groups for this study is not planned.

Randomization plan will be known to the investigating physician, the Principal Investigator, the Sponsor, the regulatory authorities (in observation of serious adverse events).

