#### 8.3.3 Relation to the IMP

The Investigator should evaluate all AEs considering all accessible data, at any time new information becomes available. The definition of IMP includes the test product and the comparator drug or placebo administered during any phase of the trial.

The Investigator should assess whether, in his/her expert opinion, the relationship of the AE to the drug is suspected based on the following considerations:

Suspected:	The temporal relationship of the clinical event	
	and the study drug administration is possibl	
	while other drug products, therapeutic	
	interventions or an underlying condition do not	
	provide a sufficient explanation for the	
	observed event.	
Not suspected:	The temporal relationship of the clinical event	
	and the study drug administration is unlikely,	

or	other	drug	products,	therape	eutic
inter	ventions	or a	n underlying	g condi	tion
prov	ride a	sufficien	nt explanati	on for	the
obse	erved eve	nt.			

Causal relationship assessments are critical and must be provided for each individual AE in relation to each IMP, non-investigational medicinal product (NIMP) or other concomitant medicinal product, if applicable. Missing causality assessments will be handled as suspected to IMP by the sponsor.

AEs with a suspected relationship to NIMP or other concomitant medication (for both Sandoz and non-Sandoz products), even if non-serious, need to be reported by the investigator to the respective Country Organization Patient Safety Team (see section 8.3.5 for contact details).

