9.1. Adverse events

The safety assessment will include determining the total number, frequency, and severity of:

- 1. Adverse events (AEs), regardless of their relation to the treatment;
- 2. AEs associated or potentially associated with the medicinal product;
- 3. AEs requiring treatment discontinuation.

Adverse events will be coded using the MedDRA nomenclature in the latest version. These will be represented by the preferred term (PT) and systemic organ class (SOC).

Methods of descriptive statistics will be used to represent the results. Comparison of the incidence of new cases of AE in the study groups will be carried out using Fisher's exact test or Pearson's χ^2 test, depending on the number of observations in one cell (< 5 or \geq 5).

Changes in the results of laboratory tests over time and the incidence of abnormal test results (based on the reference values of the central laboratory) will be summarized by groups, and a comparison will be made between the groups using appropriate tests for quantitative and qualitative data.

Safety data will be analyzed using the methods designated for the application of efficacy data evaluation.

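### The protocol's only gastrointestinal-focused safety analysis counts just the events that unblinded investigators call related, and neither document specifies an all-cause, patient-level version

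*Protocol*

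**What the plan says.** **The gastrointestinal analysis.** Protocol 9.1.4 limits the separate analysis of gastrointestinal disorders to those "regarded by the Investigator as related to the study therapy, will be analyzed separately". Protocol 4.1 (Safety Measurements) has the same restriction: complaints "considered as related to the study therapy by the investigator, will be analyzed separately". The synopsis agrees. All three define the events through a standardised MedDRA query, and none names the query.

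**Who judges relatedness.** Protocol 8.3.3: "The Investigator should assess whether, in his/her expert opinion, the relationship of the AE to the drug is suspected". Protocol 4.4.2: "Blinding within this study is not planned". Protocol 4.10: "Randomization plan will be known to the investigating physician, the Principal Investigator, the Sponsor". The person who decides whether an event enters the analysis therefore knows the arm.

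**The general safety analysis.** The first safety item in protocol 9.1.4 is "adverse events (AEs), regardless of their relationship to the treatment", and in SAP 9.1 it is "Adverse events (AEs), regardless of their relation to the treatment". Protocol 4.1 lists the frequency and severity of all adverse events among its endpoints and tests all-event incidence between arms with Fisher's exact or chi-square test.

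**What the SAP carries forward.** SAP 9.1 has three categories: all events, related events, and events requiring discontinuation. Events are presented by system organ class and preferred term. SAP 9.2 foresees no further safety endpoint. The adverse event shells in SAP Appendix 1 are Table 1 (all events by class and term, by arm, with a Fisher p-value) and a generic set called Tables N, which includes relatedness by class and term. None is based on a MedDRA query.

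**The concern.** Gastrointestinal reactions make up most of the known reactions listed for both products, and they are the only class that the protocol analyses on its own. A reader interested in how the two brands compare on stomach and bowel symptoms will look there.

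What that analysis counts is the product of two things: how often the events occur, and how often an investigator who knows the brand attributes them to it. If attribution differs between the new and the reference brand, the related-only rates can differ when the true rates are equal, or agree when the true rates differ. Randomization does not protect against this, because the filter is applied after allocation and with knowledge of it.

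The SAP leaves out the query grouping without giving a reason. The protocol still requires the analysis, the SAP does not define it, and it is unclear which gastrointestinal comparison will be reported.

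**Working it through.** The plan states no figure on this point, so there is none to reproduce. The check has two parts.

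**1. The available gastrointestinal outputs side by side**

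| Source | Filtered by relatedness? | Grouped by query? | Patient-level percentage? |
|---|---|---|---|
| Protocol 9.1.4, 4.1 and synopsis, separate analysis | Yes | Yes, query not named | Not stated |
| SAP Appendix 1, adverse events Table 1 | No | No, class and term rows | No |
| SAP Appendix 1, Tables N (relatedness) | Shown by category | No, class and term rows | No |

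Table 1 has two percentage columns. One is a share of all adverse events; the other is a share of the adverse events on that product. Neither has treated patients as its denominator. A share of events can be equal in both arms even when one arm has far more events of every kind. The shell does not say whether its count column holds events or patients.

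The class-level row is also not the same as a symptom query. Both product texts in protocol 2.1 list discoloured feces as a gastrointestinal reaction in 23% of patients and describe it as not clinically significant. If it is recorded as an adverse event here, that is about 0.23 × 168 = 39 patients per arm, enough to dominate the class row. The preferred-term rows have the opposite problem: they split nausea, diarrhea and indigestion into separate counts.

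**2. How far unequal attribution could move the related-only comparison**

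Inputs: 168 patients per arm (protocol 9.3), all treated. The true rates and attribution proportions are assumptions; the documents give neither.

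Related rate = true rate × attribution. With the same true rate p in both arms, the spurious difference is p × (attribution in the test arm − attribution in the reference arm). For 60% against 80% this is −0.20 × p. The last column is the chance that Fisher's test gives p < 0.05, from exact binomial enumeration.

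| True rate, both arms | Attribution, test / reference | Related rates | Spurious difference (points) | Fisher p < 0.05 |
|---|---|---|---|---|
| 10% | 70% / 70% | 7% / 7% | 0 | 2.9% |
| 20% | 70% / 70% | 14% / 14% | 0 | 3.5% |
| 30% | 70% / 70% | 21% / 21% | 0 | 3.7% |
| 10% | 60% / 80% | 6% / 8% | −2 | 7.3% |
| 20% | 60% / 80% | 12% / 16% | −4 | 14.8% |
| 30% | 60% / 80% | 18% / 24% | −6 | 23.0% |
| 10% | 50% / 80% | 5% / 8% | −3 | 14.1% |
| 20% | 50% / 80% | 10% / 16% | −6 | 31.8% |
| 30% | 50% / 80% | 15% / 24% | −9 | 50.1% |

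The same mechanism can hide a difference. With 60% against 80% attribution, the related rates are equal whenever the true test rate is 0.80 / 0.60 = 1.33 times the reference rate. For example, 20% × 1.33 = 26.7% in the test arm gives 26.7% × 0.60 = 16%, and 20% × 0.80 = 16% in the reference arm.

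A comparison of events of any cause does not contain the attribution term, so none of these shifts applies to it.

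**The case against.** The strongest reply is that the related-only analysis is an addition to an unfiltered one. Events of any cause come first in both documents, are tested between arms, and are a listed endpoint. This is correct. A reader might infer that the main tolerability comparison is filtered by an open-label judgement because the SAP drops the gastrointestinal analysis. The documents do not support that. No section gives the analysis that status. The omission also works the other way: what the SAP retains is the unfiltered Table 1, so leaving the related-only analysis out reduces exposure to attribution bias. Nor have related gastrointestinal events disappeared from the SAP, since Tables N tabulate relatedness by class and term. Only the query grouping is missing.

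Second, the documents give no reason to expect a large attribution gap. Both arms take the same active substance at the same dose, and the two product texts list the same gastrointestinal reactions. Protocol 8.3.3 sets criteria for relatedness and treats a missing assessment as suspected. This also stands, and it is why the figures above are illustrations of what is possible.

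Third, removing the filter does not make the comparison unbiased. Patients also know their product, and events come from questioning and spontaneous reports (protocol 8.3.4). Open-label reporting bias remains under any version of the analysis.

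The reply does not remove the gap shown in the first table. Table 1 supplies an unfiltered class row, but not the proportion of treated patients with a gastrointestinal event, and not the symptom grouping that the protocol intended.

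**Conclusion.** A minor point that holds within limits. The protocol's only gastrointestinal-focused analysis depends on causality judgements made with knowledge of the arm. Its query is unnamed, and the SAP does not carry the grouping forward. Neither document specifies an all-cause, patient-level, query-grouped comparison.

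The possible distortion is 2 to 6 points if true rates are 10% to 30% and attribution is 60% against 80%. It reaches 9 points at a 30% true rate with 50% against 80% attribution. It is zero if attribution is equal. All of these inputs are assumed. They show that bias is possible, not that it occurred or is likely. The general adverse event comparison and the primary efficacy analysis are not affected.

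**What to change.** In protocol 9.1.4, with matching text in 4.1 and the synopsis, and in SAP 9.1:

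- Name the MedDRA query that defines gastrointestinal disorders.
- Compare between arms the number of treated patients with at least one event from that query, regardless of relatedness, in the safety population. Report the risk difference with a 95% CI.
- Keep the investigator-related subset as a supportive analysis.
- State that reporting in an open-label trial can still differ by arm, so the result is descriptive.
- Add one shell to SAP Appendix 1 with treated patients per arm as the denominator.

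The cost is one paragraph and one table. No new data are needed: protocol 8.3.4 already requires every adverse event to be recorded, and protocol 9.1 already provides for MedDRA coding. The text should be settled before the arms are compared, including at the interim analysis, which also assesses safety.
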